8.2 Safety and Other Assessments

Unanticipated problems posing risks to subjects will be reported to the Penn IRB using the form: "Unanticipated Problems Posing Risks to Subjects or Others Including Reportable Adverse Events" or as a written report of the event (including a description of the event with information regarding its fulfillment of the above criteria, follow-up/resolution and need for revision to consent form and/or other study documentation).

Copies of each report and documentation of IRB notification and receipt will be kept in the Clinical Investigator's study file.

The following events are reportable to the Penn IRB:

- Breach of confidentiality
- Change to the protocol taken without prior IRB review to eliminate apparent immediate hazard to a research participant.
- Protocol violation (meaning an accidental or unintentional deviation from the IRB approved protocol) that in the opinion of the investigator placed one or more participants at increased risk or affects the rights or welfare of subjects.

This study will be unblinded. The Sponsor monitors the safety and clinical efficacy of the protective device and analyze outcome measures to determine whether or not the trial should proceed or be aborted. Study questionnaires will be completed after training and questionnaires on device utilization will be completed after each device use and transferred into electronic format. Dedicated research personnel will be present for each device. Data collection and monitoring will occur remotely. The trial will continue if and only if no clinically significant adverse events or unanticipated device failures are observed. The interval assessment of design changes based on subject feedback will not be incorporated into the current design used for this study. Subjects would be informed of device modifications and updated user instructions and training would be provided.

It is the responsibility of the Sponsor to oversee the safety of the study at their site. This safety monitoring will include careful assessment and appropriate reporting of adverse events as noted above, as well as the construction and implementation of a site data and safety-monitoring plan. Medical monitoring will include a regular assessment of the number and type of adverse or serious adverse events.

Electronic data will be stored on an institutionally secured and managed drive and/or in the Velos/PennCTMS system. Only authorized study personnel will have access.

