8.3 Adverse Events and Serious Adverse Events

8.3.1 Definitions

8.3.1.1 Adverse Event/Adverse Device Effect

An **adverse event** (AE) or adverse device effect (ADE) is any untoward medical occurrence (sign, symptom, or experience) that develops or worsens in severity associated with the use of the biocontainment device, whether or not considered intervention related. Intercurrent illnesses or injuries should be regarded as adverse events. A pre-existing condition should be recorded as an adverse event if the frequency, intensity or the character of the condition changes. Abnormal results of the intervention are considered to be adverse events if the abnormality:

- results in study withdrawal
- is associated with a serious adverse event
- is associated with clinical signs or symptoms
- leads to additional treatment or to further resource utilization (diagnostic tests/procedures)
- is considered by the investigator to be of clinical significance

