8.3.4 Adverse Event Reporting

Reporting Period

Adverse events will be reported from the time of informed consent until study completion.

Investigator Reporting: Notifying the Study Sponsor and via the Medical Director.

Every SAE/UADE, regardless of suspected causality (e.g., relationship to study product(s)) must be reported to the medical director and sponsor within 24 hours of learning of its occurrence.

Recurrent episodes, complications, or progression of the initial SAE must be reported to the Sponsor as a follow-up to the original episode within 24 hours of the investigator receiving the follow-up information. A SAE/UADE considered completely unrelated to a previously reported one should be reported separately as a new event.

Send the SAE report to the Medical Director.

New information regarding the SAE or UADE will be reported as it becomes available and in the same manner that the initial SAE (i.e., MedWatch form). The investigator must follow the event to resolution or until the event is deemed and documented irreversible, whichever is longer.

Investigator Reporting: Local Reporting Requirements

The investigator will report AEs/ADEs and SAEs/UADES to the IRB/EC of record and other local regulatory groups per the local requirements. Additional reporting/requirements include: failure to obtain ICF, device recall/repair/disposal, change in risk determination, or FDA or IRB withdrawal of the study.

8.3.5 *Serious Adverse Event Reporting*

The study PI will immediately report to the sponsor any serious adverse event or UADE, whether or not considered biocontainment device related, including those listed in the protocol and must include an assessment of whether there is a reasonable possibility that the biocontainment device caused the event.

New information regarding the SAE or UADE will be reported as it becomes available and in the same manner that the initial SAE/UADE (i.e. SAE form). All serious adverse events (SAEs) and UADEs will be followed until satisfactory resolution or until the site investigator deems the event to be chronic or the participant is stable. Other supporting documentation of the event may be requested by the study sponsor and should be provided as soon as possible.

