9 STATISTICAL CONSIDERATIONS

9.1 *Statistical Hypotheses*

We hypothesize that the biocontainment device will be a safe and effective option for performing airway procedures in patients while also providing additional protection during an aerosol generating procedure.

Primary Efficacy Endpoints:

1. We hypothesize that the time to perform an airway procedure with the biocontainment device will be equivalent to time for airway procedure without the biocontainment device. Alternatively, there will be prolonged airway procedures times with the device. This endpoint will be analyzed every two weeks.
2. We anticipate that the number of AEs or ADEs will be low and will also decrease over time. This endpoint will be analyzed on a weekly basis.

Secondary Efficacy Endpoints:

1. We hypothesize that the median Likert ratings for User subject device comfort will be weighted toward “strongly agree”. Alternatively, we will see ratings favoring “neutral” or “disagree” for user subject device comfort.
2. We hypothesize that the median Likert ratings for User subject additional healthcare burden comfort will be weighted toward “strongly disagree”. Alternatively, we will see ratings favoring “neutral” or “agree” on increased healthcare burden.
3. The median Likert ratings for the Patient Experience survey will be weighted toward minimal patient discomfort or anxiety. Alternatively, we will see ratings favoring increased patient discomfort or anxiety inside the device.
3. We anticipate that the median Likert ratings of the patient experience post-survey will indicate overall good user comfort and low levels of anxiety or claustrophobia in the device.

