9.4.5 Planned Interim Analyses

An interim analysis will be performed after 50% enrollment (approximately 4 weeks) on primary and secondary outcomes. If the total number of AEs or ADEs is trending upward over time, the study would be paused until further assessment of AE/ADEs by the study Sponsor or their qualified designee would be performed as described in [Section 8](#).

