10.1.2 Study Discontinuation and Closure

This study may be temporarily suspended or prematurely terminated by the Sponsor or the PI at any site if there is sufficient reasonable cause. Written notification, documenting the reason for study suspension or termination, will be provided by the suspending or terminating party to the study participants, investigator, the Investigational New Drug (IND) or Investigational Device Exemption (IDE) sponsor and regulatory authorities, if applicable. If the study is prematurely terminated or suspended, the Principal Investigator (PI) will promptly inform study participants, the Institutional Review Board (IRB), and sponsor and will provide the reason(s) for the termination or suspension. Study participants will be contacted, as applicable, and be informed of changes to study visit schedule.

Circumstances that may warrant termination or suspension include, but are not limited to:

- Determination of unexpected, significant, or unacceptable risk to participants
- Demonstration of efficacy that would warrant stopping
- Insufficient compliance to protocol requirements
- Data that are not sufficiently complete and/or evaluable
- Determination that the primary endpoint has been met
- Determination of futility
- Determination of SAE associated with device functionality as described in [Section 7](#)
- PI Contractual or GCP Breach

Study may resume once concerns about safety, protocol compliance, and data quality are addressed, and satisfy the sponsor, IRB and/or Food and Drug Administration (FDA).]

In terminating the study, the Sponsor and the Principal Investigator will assure that adequate consideration is given to the protection of the subjects' interests.

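### Section 8.2 lets the trial continue only with zero clinically significant adverse events, related or not, which conflicts with the trend-based pause in 9.4.5; one governing rule is needed

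*Combined protocol and SAP*

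**What the plan says.** The combined protocol and SAP deals with trial-level continuation in several places.

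- **Section 8.2** sets the condition: "The trial will continue if and only if no clinically significant adverse events or unanticipated device failures are observed". Earlier in the same paragraph the sponsor is to "analyze outcome measures to determine whether or not the trial should proceed or be aborted", which is a matter of judgement.
- **Section 8.3.1.1** defines an AE or ADE as an untoward occurrence "associated with the use of the biocontainment device, whether or not considered intervention related", and adds intercurrent illnesses and injuries. It mentions clinical significance only as something the investigator judges and gives no working definition.
- **Section 8.3.4** sets the window: "Adverse events will be reported from the time of informed consent until study completion".
- **Section 9.4.5**, for the look at 50% enrolment, says: "If the total number of AEs or ADEs is trending upward over time, the study would be paused", pending assessment by the sponsor or a designee.
- **Section 10.1.2** is discretionary and open-ended: "Circumstances that may warrant termination or suspension include, but are not limited to". Its SAE item is tied to device functionality, and it allows the study to resume once concerns are addressed.
- **Section 7.2** lets an investigator withdraw a patient because of an AE, and says that device-arm patients who are withdrawn after using the device will be replaced.

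This point concerns the adverse-event part of the 8.2 condition, not the device-failure part.

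**The concern.** Read as written, the 8.2 condition looks only at whether a clinically significant AE has been observed. It does not use the relatedness grade that 8.3.2.2 requires for every AE, and it has no count or rate. Patients are ASA I to III and are having general anaesthesia, so a clinically significant event unrelated to the device is possible, and one would be enough.

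Section 9.4.5 would handle the same situation differently. The study is unblinded, and 10.1.5 places safety oversight with the sponsor and medical director. If such an event occurs, either the trial halts short of its 100 device and 50 control procedures, at least for a time, or it carries on against a written condition. Which section governs would then be settled after the data had been seen.

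**Working it through.** **Step 1. The rules side by side, read literally.**

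| Situation | Section 8.2 | Section 9.4.5 |
|---|---|---|
| One clinically significant event, graded unrelated; total count not rising | Trial does not continue | No ground to pause |
| Rising count of minor expected events (such as anxiety); none clinically significant | Trial continues | Pause for assessment |

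The sections differ in both rows. The second row follows because the 8.2 condition is worded as sufficient as well as necessary. Section 10.1.2 would leave either case to judgement and would allow resumption.

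**Step 2. How often the 8.2 condition would be triggered with no device effect.** The plan states no such probability, so there is no figure to reproduce.

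Inputs:
- N = 100 device procedures, or N = 150 in total (section 1.3). The 8.3.1.1 definition refers to events associated with device use, so N = 100 is the better-supported base. N = 150 applies if control-arm events also count.
- r = probability that a patient has a clinically significant AE unrelated to any device effect. The documents give no value, so a range from 0.1% to 5% is assumed.

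Formula: P(at least one event) = 1 − (1 − r)^N.

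Example at r = 1%: 1 − 0.99^100 = 1 − 0.366 = 63%, and 1 − 0.99^150 = 1 − 0.221 = 78%.

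| Assumed r | N = 100 | N = 150 |
|---|---|---|
| 0.1% | 9.5% | 14% |
| 0.25% | 22% | 31% |
| 0.5% | 39% | 53% |
| 1% | 63% | 78% |
| 2% | 87% | 95% |
| 5% | 99% | >99.9% |

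**Step 3. Break-even rates.**
- Even odds of triggering: r = 1 − 0.5^(1/N), which is 0.69% for N = 100 and 0.46% for N = 150.
- A chance of at most 10%: r = 1 − 0.9^(1/N), which is about 0.105% for N = 100 and 0.07% for N = 150.

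The calculation treats patients as independent with a common rate. It leaves out the device-failure trigger, which could only raise the chance.

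**The case against.** The best defence is that zero tolerance may be deliberate for a device never before used in a healthcare setting, and that 8.2 and 9.4.5 count different things. Section 8.2 concerns clinically significant events. Section 9.4.5 concerns all AEs and ADEs, including the minor expected ones in 8.3.2.3. On this view 8.2 is a stricter rule sitting on top of 9.4.5. Section 8.2 also calls for a site data and safety-monitoring plan, which is not among the documents and may hold the operational detail.

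Part of this stands. The sponsor may choose a zero-event condition, and the two sections do use different counts. But different counts do not tell a reader which section governs when they point to different actions, as in both rows of Step 1. A separate plan could clarify this, but the protocol's own sections would still disagree.

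The conflict with 10.1.2 is softer, because its list is not exhaustive and an extra trigger does not contradict it. The replacement provision in 7.2 is also only indirect evidence, since a patient might be withdrawn for an AE that is not clinically significant.

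A reader might also cite section 9.1: "We anticipate that the number of AEs or ADEs will be low and will also decrease over time". That does not show that the trial is expected to continue after an event that triggers 8.2, because a falling total is compatible with no clinically significant event at all.

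**Conclusion.** The conflict between 8.2 and 9.4.5 stands on the text alone and needs no assumed rate. So does the absence of a relatedness qualifier in 8.2, set against an AE definition that takes in unrelated events.

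The size is conditional. With no device effect, the 8.2 condition is more likely than not to be triggered only if clinically significant background events occur in more than about 0.7% of device patients, or about 0.5% of all patients if the control arm counts. What counts as clinically significant is left to judgement, so the documents do not place the rate on either side of those values.

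Three stronger readings are tempting but not supported:

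- **That the rule would probably stop a trial of a harmless device.** This needs a background rate. The documents say only that AEs should be few, and at 0.1% the chance is 9.5% (N = 100) or 14% (N = 150).
- **That one event ends the trial for good.** Section 8.2 does not say terminate, and 10.1.2 allows resumption. The figures are chances of triggering.
- **That the rule cannot distinguish a harmful device from a harmless one.** A device that adds events raises r and with it the chance of triggering. The supportable point is that the rule may be triggered often without any device effect at some plausible rates.

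**What to change.** Before enrolment, reconcile 8.2, 9.4.5 and 10.1.2 into one governing trial-level rule, with each section referring to it. The rule should state whether events graded unrelated under 8.3.2.2 count toward it and whether control-arm events count. Report its chance of triggering under an assumed rate with no device effect, over a range if the rate is uncertain. The threshold and the clinical action are for the sponsor and medical director to set; nothing here favours one of the existing rules.

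The cost is a wording amendment and a short calculation, with no extra patients. If control-arm events are to count, the sponsor should check that they are captured comparably: the Quality Use Survey follows days of device use, and the patient survey goes only to patients randomized to the device (section 8.1).

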8.3 Adverse Events and Serious Adverse Events

8.3.1 Definitions

8.3.1.1 Adverse Event/Adverse Device Effect

An **adverse event** (AE) or adverse device effect (ADE) is any untoward medical occurrence (sign, symptom, or experience) that develops or worsens in severity associated with the use of the biocontainment device, whether or not considered intervention related. Intercurrent illnesses or injuries should be regarded as adverse events. A pre-existing condition should be recorded as an adverse event if the frequency, intensity or the character of the condition changes. Abnormal results of the intervention are considered to be adverse events if the abnormality:

- results in study withdrawal
- is associated with a serious adverse event
- is associated with clinical signs or symptoms
- leads to additional treatment or to further resource utilization (diagnostic tests/procedures)
- is considered by the investigator to be of clinical significance

8.3.1.2 Serious Adverse Events (SAE)

Adverse events are classified as serious or non-serious.

A **serious adverse event** is any AE that is:

- fatal
- life-threatening
- requires or prolongs hospital stay
- results in persistent or significant disability or incapacity
- a congenital anomaly or birth defect
- an important medical event
- required intervention to prevent permanent impairment or damage to participant or subject

Important medical events are those that may not be immediately life threatening, but are clearly of major clinical significance. They may jeopardize the subject, and may require intervention to prevent one of the other serious outcomes noted above. For example, drug overdose or abuse, a seizure that did not result in inpatient hospitalization, or intensive treatment of bronchospasm in an emergency department would typically be considered serious.

All adverse events that do not meet any of the criteria for serious should be regarded as **non-serious adverse events**.

8.3.1.3 Unanticipated Adverse Device Effect (UADE)

An unanticipated adverse device effect (UADE) is any serious adverse effect on health or safety, or any life-threatening problem or death caused by, or associated with, a device, if that effect, problem, or death was not previously identified in nature, severity, or degree of incidence in the investigational plan or application, or any other unanticipated serious problem associated with a device that relates to the rights, safety, or welfare of subjects.

8.3.2 Classification of an Adverse Event

8.3.2.1 Severity of Event

Adverse events will be classified based on the defined grading system:

- Mild: events require minimal or no treatment and do not interfere with the participant's daily activities
- Moderate: events result in low level of inconvenience or cause some inference with functioning
- Severe: events interrupt a participant's usual daily activity. Severe events are usually potentially life-threatening or incapacitating. Please note, the term "severe" does not necessarily equate to "serious".

8.3.2.2 *Relationship to Study Intervention*

All adverse events (AEs) and ADEs must have their relationship to the study device assessed by the PI who examines and evaluates the participant based on temporal relationship and his/her clinical judgment. The degree of certainty about causality will be graded using the categories below. In a clinical trial, the study product must always be considered.

- Definitely Related – The AE/ADE is known to occur with the device.
- Probably Related – There is a reasonable possibility that the device caused the AE, or there is a temporal relationship between the device use and event. Reasonable possibility means that there is evidence to suggest a causal relationship between the device and the AE/ADE.
- Possibly Related - There is a possibility that the device caused the AE, or there is a temporal relationship between the device use and event. There is no evidence to suggest a causal relationship between the device and the AE/ADE but an alternate etiology has not yet been established.
- Unrelated – There is not a reasonable possibility that the use of the device caused the event, there is no temporal relationship between the use of the device and event onset, or an alternate etiology has been established.

8.3.2.3 *Expectedness*

Expected adverse events associated with this study that will be tracked and reported include:

1. Minor injury to the patient subject or provider
2. Patient claustrophobia
3. Patient anxiety
4. Difficulty performing intubation with the device in place
5. Need to remove the biocontainment device to safely perform intubation

Potential SAEs associated with this study would include:

1. Major physical injury to patient or provider due to device failure.

A UADE for this device would be breakdown or malfunction of the device during use.

The Sponsor medical director is responsible for determining whether an adverse event (AE) or ADE is expected or unexpected. An AE or ADE will be considered unexpected if the nature, severity, or frequency of the event is not consistent with the risk information listed in the Investigational Plan.

8.3.3 Time Period and Frequency for Event Assessment and Follow-Up

Safety will be assessed by monitoring and recording potential adverse effects using the quality use survey and the patient survey questionnaire as defined in [Section 1.3](#). Participants will be monitored by these questionnaires. Any adverse events/ADEs are captured and shared with study PIs and the Sponsor. AEs and SAEs will be assessed for daily and completeness of surveys (data integrity) will be assessed weekly.

The investigator will seek information on adverse events by non-directive questioning. Adverse events may also be detected when they are volunteered by the clinician utilizing the device. Information on all adverse events will be recorded in the source documentation. To the extent possible, adverse events will be recorded as a diagnosis and symptoms used to make the diagnosis recorded within the diagnosis event.

As much as possible, each adverse event or follow-up information will be evaluated to determine:

1. Severity grade (as described in [Section 8.3.2.1](#) above)
2. Duration (start and end dates)
3. Relationship to the study treatment or process – (As described in [Section 8.3.2.2](#) above)
4. Expectedness to study treatment or process – [Unexpected – if the event severity and/or frequency is not described in the investigator brochure (if applicable) or protocol].
5. Action taken with respect to investigational device or process (none, permanently discontinued, unknown, not applicable)
6. Whether the event is serious

Once an adverse event is detected, it should be followed until its resolution or until it is judged to be permanent, and assessment should be made weekly (or more frequently, if necessary) of any changes in severity, the suspected relationship to the study treatment, the interventions required to treat it, and the outcome.

